1.4 Anticipated duration of the clinical investigation

Active participation will last no more than the 90 days after the leads are placed. However, as several pre-surgical and post-removal procedures are required (e.g. balance and gait testing, pain questionnaires, blood work, MRSA screening, EKG, MRI), total duration of the subject's participation in this study across all visits (including screening, experimental testing, and follow-up surveillance) may last up to 9 months.

2.0 Clinical protocol

2.1 Title of clinical protocol

“Spinal Cord Stimulation for Restoration of Function in Lower-Limb Amputees”

2.1.1 Protocol number

University of Pittsburgh, STUDY19010019

2.1.2 Version number and date

Modification Version: STUDY19010019

Approval Date: 8/2/2022

IRB Expiration Date: 8/1/2023

2.2 Study design

2.2.1 General study design

This study is a prospective, non-randomized, open-label, descriptive, interventional study.

2.2.2 Study design schematic

Figure 1 illustrates the proposed study design. Procedures are discussed in **Section 2.4**.

[figure not shown]

Figure 1. Study design schematic

2.3 Subject selection

2.3.1 General characteristics of the proposed subject population

The subjects for this study will be individuals between the ages of 22-70 with an amputation of one lower limb at a level between the ankle and knee joints. Subjects should be at least 6-month post-amputation at the time of study participation. To ensure their safety during participation, subjects will be screened to ensure that they have no serious diseases or disorders that could be complicated by participation. Due to the greater than minimal risk designation of the study, we will be using adult subjects to ensure that participants are mature enough to understand the tasks, as well as the risks, involved; further, we want to ensure that the central nervous system is fully developed prior to enrollment in this study.

2.3.2 Anticipated number of research subjects

Up to 15 total subjects may undergo research procedures, with the goal of completing all experiments with 10 subjects. Recruitment rates will be monitored by our DSMB. Because it is possible that a subject may enroll and then be determined to be ineligible, the

maximum number of subjects enrolled may exceed the number who undergo device placement. Subjects will be enrolled as necessary to maintain the target number of subjects. Recruitment will not begin until we have received all approvals.

2.3.3 Inclusion criteria

- 1) Subjects must have an amputation of one lower limb, at a level between the ankle and knee joints. Minor amputation of the contralateral limb (i.e. toes or partial foot) is not exclusionary.
- 2) Subjects must be over 6-month post-amputation at the time of lead placement.
- 3) Subjects must be between the ages of 22 and 70 years old. Participants outside this age range may be at an increased medical risk and have an increased risk of fatigue during testing.
- 4) Subjects must have used their current prosthesis for at least 6 months and achieved at least K-1 ambulator status at the time of lead placement, as determined by the Amputee Mobility Predictor.

2.3.4 Exclusion criteria

- 1) Subjects must not have any serious disease or disorder that could affect their ability to participate in this study.
- 2) Female subjects of childbearing age must not be pregnant or breast-feeding.
- 3) Subjects must not be receiving medications that affect blood coagulation.
- 4) Subjects must not have an allergy to contrast medium or renal failure that could be exacerbated by the contrast agent used in MRIs. For this study, renal insufficiency will be determined through blood work and defined as BUN of 30 mg/dl or more and Creatinine of 1.5 mg/dl or more.
- 5) Subjects may not have a hemoglobin A1c level above 8.0 mg/dl at time of implant.
- 6) Subjects may not have any implanted medical devices that are not cleared for MRI.
- 7) Subjects with a T-Score higher than 63 on the 18-question Brief Symptoms Inventory (BSI-18) who have undergone discussions with and been deemed unsuitable by the Principal Investigator, a study physician, and a psychologist
- 8) Subjects may not have a cardiac pacemaker.
- 9) Subjects may not have a cardioverter defibrillator.
- 10) Subjects may not be currently receiving diathermy therapy.
- 11) Subjects may not have an implanted infusion pump.
- 12) Subjects may not be immunosuppressed or currently receiving immunosuppressive medications.
- 13) Subjects may not have a profession (e.g. radiology technologist) or medical condition (e.g. remissory cancer involved regular follow-up x-rays) that would increase radiation exposure in the 12 months prior to starting or after ending participation in the study.

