2.4.2.2 Pre-operative physical and screening

Prior to the lead placement procedure, participants will undergo several screening procedures, including x-rays and clinical lab workups. For diabetic participants with elevated hemoglobin A1c levels (greater than 8.0 mg/dl), we may perform repeated blood draws within the 6 months following consent to ensure implant does not pose a risk of infection. If the participant's levels remain consistently above 8.0 mg/dl within the 6-month period following consent, we will not schedule lead placement, and will withdraw the participant from the study.

If the subject does not have an elevated A1c level, within two weeks prior to the lead placement procedure, we will perform: pre-operative chest x-ray; a routine urinalysis with microscopy; a complete blood count with differential and platelets; a prothrombin time and international normalized ratio; an activated partial thromboplastin time; iron, prealbumin, albumin, and hemoglobin A1c levels; a vitamin D 25-OH screen for deficiency/toxicity; urine pregnancy screen; and a MRSA screen. If study physicians suspect the subject may have renal insufficiency, which would prevent the use of gadolinium-based contrast agents, we may also perform blood urea nitrogen (BUN) and creatinine (Cr) testing. In the case of inconclusive test results and at the discretion of the study physicians, we may need to ask a participant for repeated sample collection. All lab work and repeated testing will be performed through UPMC.

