2.4.2.8 Prophylactic antibiotics

We will follow the standard clinical procedures to minimize the risks associated with percutaneous placement of electrodes. Prophylactic antibiotics will be administered intravenously 30 minutes before surgery and may be maintained as directed by a study physician and their clinical team. We will generally use cefazolin for this procedure; however, if the subject tests positive for or has a charted history of MRSA, intravenous vancomycin will also be administered. If the subject has a severe penicillin allergy, vancomycin will be administered without cefazolin. We have excluded pregnant females and those with renal failure (see **Section 2.3.4**) as they may be at an increased risk for complications resulting from administration of the antibiotics. Sterile silver dressings will

be applied to the insertion site, covering the protruding leads, to minimize the risk of infection. These procedures will greatly minimize the risk of infection and may vary based on the study physicians' clinical judgment and input from Infectious Disease experts.

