The magnet utilized for MRI will make intermittent loud knocking noises that could cause discomfort in some subjects. The subject may experience feelings of anxiety or claustrophobia during the MRI scan. There is also a risk of the MRI scanner attracting metal objects. There is a risk of loosening of ferromagnetic objects that are affixed to bone. There is a risk of tissue heating for metallic implants. The contrast agent used during these MRI's, gadolinium, is FDA-approved and used routinely for MRI exams. The injection of contrast may cause discomfort, tingling, or warmth in the lips, metallic taste in the mouth, tingling in the arms, nausea, or headache. These symptoms occur in less than 1% of people and go away quickly. There is a small risk of an allergic reaction to gadolinium; however, a severe allergic reaction occurs in less than one in 300,000 individuals. Insertion of the needle to inject the gadolinium may cause minor pain, bruising, and/or infection at the injection site. People with severe kidney failure who receive gadolinium are at risk of developing Nephrogenic Systemic Fibrosis/Nephrogenic Fibrosing Dermopathy (NSF/NFD). This disease causes fibrosis, which is the formation of too much connective tissue in the skin and internal organs throughout the body. People develop skin thickening that may prevent bending and extending joints, resulting in decreased movement of the joints. The skin changes can cause feelings of burning, itching, and pain that can be severe. In addition, people may experience fibrosis that spreads to other parts of the body such as the diaphragm, muscles in the thigh and lower abdomen, and the lining of blood vessels in the lung. NSF/NFD is a serious progressive disease and can result in death. If the subject has severe kidney failure and receives gadolinium, the risk of developing NSF/NFD is 1-5%. We may require a blood sample (about 1 tablespoon) to check kidney function before gadolinium contrast is utilized. There is evidence that repeated MRI scans with gadolinium can result in some accumulation of it in the brain. The significant of this and possible effect on health is not known.

Steps taken to minimize these risks:

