Steps will be taken to minimize potential discomforts due to noise in the MRI, such as wearing earplugs and informing the subject beforehand about these discomforts. Two-way communication will be available throughout the scan in case the subject experiences feelings of anxiety or claustrophobia. The study team, as well as the staff at the MRI center(s), will administer standard screening procedures prior to the scan to ensure the subject's safety. Metallic implants, such as pacemakers or permanent piercings, are considered contraindications for MRI and may exclude potential participants. Any implanted metal will be investigated prior to MRI to determine its safety. Participants will be asked to notify a doctor, nurse, or technologist if they are allergic to gadolinium, if they have any kidney problems, or if they experience any other side effects. Individuals with renal failure or dysfunction will be excluded from study participation. A physician will be available during this procedure to administer any necessary care if side effects do occur, and to determine when or if the injection of gadolinium should be stopped.

Mechanical and/or Electrical Stimulation of the Residual and Contralateral Limbs:

There are minor risks associated with the electrical and mechanical stimulation of the residual and contralateral limbs. These include uncomfortable sensations and irritation of the skin. As with EMG signal recording, sticky electrodes may be attached to the skin during electrical stimulation; these may cause skin irritation.

Steps taken to minimize these risks:

To avoid discomfort and skin irritation, we will ensure that the subject is aware that they may request to stop testing at any time. Further, we will work with the subject to ensure that we avoid repeating application of stimulation to the limbs that is excessively uncomfortable.

Observing a Virtual 3-D Environment:

Nausea or dizziness may result from wearing 3-D glasses in a virtual environment.

Steps taken to minimize these risks:

This risk will be mitigated by providing frequent breaks and adjusting task difficulty.

Two-Week Community-Use Trial:

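### Exclusion 4 counts renal insufficiency only when BUN and creatinine are both raised, and the blood tests it relies on are optional

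*Combined protocol and SAP*

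**What the plan says.** Exclusion 4 in section 2.3.4 has two sentences. The first bars contrast allergy and renal failure that the MRI contrast agent could worsen. The second makes the renal part operational: "renal insufficiency will be determined through blood work" and is "defined as BUN of 30 mg/dl or more and Creatinine of 1.5 mg/dl or more".

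Section 2.4.2.2 lists the pre-operative tests every subject will have. BUN and creatinine are not among them. They follow in a separate sentence that applies only when study physicians suspect "renal insufficiency, which would prevent the use of gadolinium-based contrast agents"; in that case "we may also perform blood urea nitrogen (BUN) and creatinine (Cr) testing".

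Section 3.1, under MRI with contrast, says: "We may require a blood sample (about 1 tablespoon) to check kidney function before gadolinium contrast is utilized". The same part states: "Individuals with renal failure or dysfunction will be excluded from study participation". Section 2.4.2.8 treats the matter as settled when it discusses antibiotics: "We have excluded pregnant females and those with renal failure", with a pointer to section 2.3.4.

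The renal term therefore varies: failure and insufficiency in 2.3.4, insufficiency in 2.4.2.2, failure in 2.4.2.8, and failure or dysfunction in 3.1.

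**The concern.** There are two gaps in the same rule.

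First, the two limits are joined by *and*. While BUN stays below 30 mg/dl, a raised creatinine does not meet the definition. That is narrower than the exclusion of renal dysfunction in section 3.1, and two screeners could classify the same subject differently depending on which section they follow.

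Second, a definition that rests on blood results can classify only subjects whose blood was tested. Under section 2.4.2.2 a subject whom nobody suspects need not be tested. Unsuspected disease is the case in which a laboratory criterion adds most to history and examination, and it is the case in which the test is not required.

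At stake is participant safety before gadolinium. Section 2.4.2.3 plans a contrast MRI unless suitable images already exist, and section 2.4.2.2 itself regards renal insufficiency as a bar to the contrast agent.

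**Working it through.** The plan gives no figure to reproduce. The check is a logical one on the rule, followed by a comparison of the rule with the test list. Below, *raised* means at or above the limit in exclusion 4.

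**Step 1: the definition.** Inputs, from section 2.3.4: BUN limit 30 mg/dl, creatinine limit 1.5 mg/dl, joined by *and*.

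| BUN (mg/dl) | Creatinine (mg/dl) | As written: both required | Alternative reading: either suffices |
|---|---|---|---|
| 30 or more | 1.5 or more | meets | meets |
| 30 or more | below 1.5 | does not meet | meets |
| below 30 | 1.5 or more | does not meet | meets |
| below 30 | below 1.5 | does not meet | does not meet |

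Three patterns have at least one raised marker. As written, the rule catches 1 of the 3; the alternative reading catches 3 of 3. These are counts of logical patterns, not of subjects.

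Example: creatinine 2.8, BUN 28. Creatinine is 2.8 / 1.5 = 1.87 times its limit. BUN is 30 - 28 = 2 mg/dl short of its limit. The definition is not met.

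No other section gives a numeric renal limit, so nothing elsewhere corrects this row of the table.

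**Step 2: the test.** Routine blood tests in section 2.4.2.2: complete blood count, prothrombin time/INR, activated partial thromboplastin time, iron, prealbumin, albumin, hemoglobin A1c, vitamin D. BUN and creatinine included: 0 of 2. The routine urinalysis may raise suspicion but measures neither serum marker.

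Compare two other exclusions that rest on a laboratory result. The hemoglobin A1c limit (exclusion 5) has its test in the routine list: "iron, prealbumin, albumin, and hemoglobin A1c levels". Pregnancy (exclusion 2) has a urine screen there. The renal criterion has neither of its tests there.

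**Step 3: the two together.** For an unsuspected subject neither value need be measured, so the definition cannot be applied under either reading of *and*. For a suspected subject the test is still only permitted; if it is done, the literal rule misses creatinine raised alone. The testing gap therefore remains even if the wording is repaired, and the wording gap remains even if everyone is tested.

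**Step 4: timing.** The routine panel falls within two weeks before lead placement. Section 2.4.2.3 does not say whether the contrast MRI comes before or after it. Adding the assays to that panel without an order rule could produce the result after contrast has been given.

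**The case against.** The strongest reply is that the numeric sentence is not the whole exclusion. The first sentence of exclusion 4 bars renal failure without a number, exclusion 1 bars serious disease, and section 3.1 bars renal dysfunction. Section 2.4.1 provides an in-person clinical evaluation and, where needed, record review. Section 3.1 adds that participants are asked to report kidney problems, that standard MRI screening is applied, and that a physician is available and can stop the contrast. Suspicion-led testing is a recognisable clinical choice. The *and* may also have been meant as a list of two separate limits. The eligibility checklist and case report forms, which might settle this, are not in the public text.

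Much of this stands. It means that a reader should not infer that the subject in the example is eligible; the documents say only that this subject misses the numeric definition. It does not close the gap. The backstops rest largely on known or suspected disease, section 2.4.1 assesses most criteria by self-report, and nothing in the text says that *and* means either.

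Other inferences are tempting but not supported:

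- **The 1-5% risk of nephrogenic systemic fibrosis in section 3.1.** It is stated for severe kidney failure and cannot be carried over to this group.
- **That the antibiotic safeguard rests on the numeric rule.** Section 2.4.8's counterpart in the procedures, section 2.4.2.8, relies on the exclusion of renal failure and points only generally to 2.3.4.
- **That a missing baseline spoils antibiotic safety monitoring.** No routine BUN or creatinine after antibiotics is planned; the metabolic panel in section 2.4.2.15 follows only suspected local infection.
- **A size based on typical BUN-to-creatinine ratios.** The documents give no ratio, so such figures would only restate the assumption.

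**Conclusion.** The point holds as a defect in an eligibility rule and its testing step, and it should be corrected. Taken literally, the definition catches one of three patterns with a raised marker, and the routine panel contains neither of the two tests. The wording finding rests on the literal reading of *and*; the testing finding does not depend on it.

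Enrolment of an affected subject is possible but not certain, because the non-numeric safeguards are real. How many of the up to 15 subjects in section 2.3.2 might be affected cannot be estimated from the documents. No endpoint, sample size or analysis changes.

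**What to change.** 1. Amend exclusion 4 so that creatinine of 1.5 mg/dl or more is sufficient on its own. State how an isolated BUN of 30 mg/dl or more is handled: either exclude, or require study-physician review before contrast is given. Both numbers are the protocol's own; making creatinine sufficient alone is a clinical decision for the investigators to confirm.
2. In section 2.4.2.2, add BUN and creatinine to the routine pre-operative blood work for every subject, with results reviewed before the contrast MRI or lead placement, whichever comes first. Change the permissive wording on the kidney-function sample in section 3.1 to match.
3. Use one renal term throughout, defined once in section 2.3.4.

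The cost is a short amendment and one inexpensive assay per screened subject, at a stage where blood is already drawn. An earlier draw may be needed if the MRI precedes the panel, and there may be an occasional extra screen failure.

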2.4 Study procedures

2.4.1 Screening procedures

We will recruit subjects from two University of Pittsburgh Institutional Review Board (IRB) approved registries developed by the Human Engineering Research Laboratories (Pitt IRB# PRO12080311) and the Department of Physical Medicine and Rehabilitation (Pitt IRB# PRO12030122). All members of the registry have agreed to participate in the registry, and have given permission to be contacted for future research. The IRB approved flyer for this study will be distributed to potential subjects according to the procedures established in the registry IRB approved protocols. The recruitment flyer will be accompanied by a letter from the registry PI/coordinator stating why they are receiving information about our study. In response to the recruitment flyer, potential subjects can directly contact the research team if interested in participating. We may also post the recruitment flyer, or other approved recruitment materials, on websites affiliated with our laboratory, the Physical Medicine & Rehabilitation Department, and the University of Pittsburgh. We may also recruit through organizations representing our subject population groups, such as assistive technology suppliers, adaptive sports organizations, amputee support groups, and amputation or other related clinics. The recruitment materials can also be made available in places such as hospitals, clinics or related events or promoted in social media or websites targeted towards individuals with amputation. Clinicians in the Department of Physical Medicine and Rehabilitation, Center for Assistive Technology, UPMC Centers for Rehab Services, and other departments at UPMC Presbyterian and UPMC Mercy who are knowledgeable about our study may distribute recruitment materials to their patients if they think they may be eligible. Clinicians or their administrative designees may also query their patient databases to find potentially eligible participants and contact these individuals directly. Individuals may contact our study team directly in response to the clinicaltrials.gov website, scientific publications, media, or other means besides our planned recruitment methods.

If an individual contacts us and is interested in this research study, we will provide that individual with information about the study (brochure, recruitment letter and/or consent form). We may conduct a phone screening to assess some of the inclusion and exclusion criteria. The initial screening can be conducted over the phone, in person, or using face-to-face video conference software, such as Skype or Facetime, for the individual's convenience. The purpose of this screening is to potentially eliminate the burden of travel on a potential participant who may not be eligible for the study. If any of the phone script screening questions indicate exclusion of that individual, the screening questions will stop at that point and the individual will be kindly told that they are not eligible for the study. If none of the phone script questions indicate exclusion from the study, then the individual will be asked to meet with the research team to further discuss study participation.

We will also use the Brief Symptom Inventory 18 (BSI-18) to screen all potential participants. Given the known increased prevalence of anxiety and depressed mood in individuals with amputation and chronic pain, it is our intent to use the BSI-18 to screen for mood symptoms as part of the consent process. The presence of symptoms, as reported on the BSI-18, will not exclude individuals from participating in the study – rather, responses given during the BSI-18 survey will be used as a tool to guide discussion

between the Principal Investigator, a study physician, and the potential subject. If an individual expresses severe depressed or anxious mood, resources will be provided to assist the individual in seeking appropriate mental health treatment. For those individuals with a BSI-18 T-score above 63, a meeting with a psychologist will be scheduled to assess their suitability for the study. Due to the sensitive nature of the questions on the BSI-18 survey, we will request that subjects complete the BSI-18 in person at the first screening visit, where appropriate clinical help, including a clinical psychologist, will be available.

Once a potential subject has been identified, the subject will be educated about the study, study goals, study tasks, and study requirements. Initial questions will be answered and they will be provided with a copy of the consent form. Initial contact may be made by any investigator, but as this study requires a surgical procedure with the inherent risks of surgery, study physicians will be available to discuss any participant questions, either in-person or via teleconferencing software, such as Skype or Facetime, prior to consent. The potential participant will also be encouraged to discuss this study and the information provided in the consent form with her or his treating physician. After the subject has met with the study team, and agreed to participate in the study, they will be consented by a physician-investigator. If the individual is capable, they will sign the consent form.

Once written informed consent is obtained, the subject is enrolled in the study and is assigned a unique subject ID. A physician-investigator will verify the eligibility of the subject by assessing most of the eligibility criteria after consent via self-report. This will be documented on an "Eligibility Checklist" form.

After informed consent and after the participant's verbal self-report of eligibility criteria, an in-person clinical evaluation will be performed. Additionally, medical records will be accessed if additional information is required to perform pre-operative planning and review pertinent medical history, allergies, medications and radiology images.

